6.4.3 Prohibited concomitant therapy

The following concomitant treatments are not allowed during the study:

- Other investigational drug or therapy.
- Medication known to affect GH or IGF-1 levels.
- Medications that might lead to QT prolongation (the discontinuation of the patient is required prior to starting the respective QT prolonging medication).

A comprehensive list of drugs that prolong the QT interval and/or induce Torsades de Pointes can be found at: <http://crediblemeds.org/everyone/composite-list-all-qt drugs/?rf=All>

- Investigational or commercial anticancer agents other than pasireotide LAR and everolimus (including chemotherapy, hormone therapy, targeted therapy, targeted or biological agents). If such agents are required for a patient, the patient must first be withdrawn from the study. The initiation of any non-protocol specific anti-tumor treatment or surgery is considered an indication of disease progression and should be recorded appropriately.
- Use of prescription medication for diarrhea. Exceptions may be made if the medication is to treat an adverse event.
- Use of dexamethasone therapy administered for nausea and/or vomiting, is prohibited during the study.
- Use of the anticoagulant medication warfarin should be avoided. Warfarin should be replaced by the use of selective Factor Xa inhibitors (rivaroxaban, apixaban, dabigatran) which are acceptable from a safety point of view since they have no effect on prothrombin time (PT), and partial thromboplastin time (PTT)
- The following drugs should also be avoided from 5 days before through to the end of the 5-HIAA collection, given their potential to affect 5-HIAA: chlorpromazine, imipramine, isoniazid, levodopa, monoamine oxidase inhibitors, methenamine, methyl dopa, phenothiazines, promethazine, and tricyclic antidepressants, acetanilid, phenacetin, glyceryl guaiacolate (component of many cough syrups), methocarbamol, and reserpine.
- Leukocyte growth factors (e.g. G-CSF and GM-CSF) are not permitted prophylactically but may be prescribed by the investigator for severe neutropenia if deemed appropriate.
- Prolonged (>2 weeks in duration) treatment with systemic corticosteroids.
- Strong CYP3A4 inhibitors and strong Pgp inhibitors are not allowed (see [Table 6-10](#)).

[figure not shown]
In addition, patients should refrain from **grapefruit juice, Seville oranges, and star fruit** as well as **the juice of these fruits** which are potent CYP3A4-inhibitor and also affect Pgp activity.

Everolimus may affect patient response to vaccinations making the vaccination less effective. As everolimus is an immunosuppressant, live vaccines should be avoided while a patient is treated with everolimus. Examples of live vaccines are: intranasal influenza, measles, mumps, rubella, oral polio, BCG, yellow fever, varicella, and TY21a typhoid vaccines.

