Grade 2 (symptomatic, not interfering with activities of daily living)	CT scan with lung windows. Consider pulmonary function testing including spirometry, DLCO, and room air O ₂ saturation at rest. Repeat at least every three cycles until return to normal limits. Consider a bronchoscopy with biopsy and/or BAL.	Symptomatic only. Prescribe corticosteroids if symptoms are troublesome.	Consider interruption of therapy, rule out infection and consider treatment with corticosteroids until symptoms improve to grade < 1. Re-initiate everolimus at a lower dose. Discontinue treatment if failure to recover within 4 wks.
Grade 3 (symptomatic, interfering with activities of daily living; O ₂ indicated)	CT scan with lung windows and pulmonary function testing including spirometry, DLCO, and room air O ₂ saturation at rest.; Repeat at least every two cycles until return to normal limits. Bronchoscopy with biopsy and/or BAL is recommended.	Prescribe corticosteroids if infective origin is ruled out. Taper as medically indicated.	Interrupt treatment until symptoms resolve to grade ≤ 1 . May restart treatment at a reduced dose (by one level), if evidence of clinical benefit. Discontinue treatment, if failure to recover within 4 wks. If toxicity recurs at grade 3, consider discontinuation.

Worst Grade Pneumonitis	Required Investigations	Management of Pneumonitis	RAD001 Dose Adjustment
Grade 4 (life-threatening, ventilatory support indicated)	CT scan with lung windows and required pulmonary function testing, if possible, includes: spirometry, DLCO, and room air O2 saturation at rest. Repeat at least every two cycles until return to within normal limits. Bronchoscopy with biopsy and/or BAL is recommended if possible.	Prescribe corticosteroids if infective origin is ruled out. Taper as medically indicated.	Discontinue treatment.

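### A corticosteroid course longer than 2 weeks, which Table 6-2 permits for pneumonitis, would breach the prohibition in Protocol Section 6.4.3

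*Protocol*

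**What the plan says.** Protocol Section 6.4.3 opens its list with "The following concomitant treatments are not allowed during the study". One bullet reads "Prolonged (>2 weeks in duration) treatment with systemic corticosteroids" and carries no qualification. Other bullets in the list do. The diarrhea bullet adds "Exceptions may be made if the medication is to treat an adverse event", and the growth-factor bullet allows use for severe neutropenia.

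Protocol Section 6.1.4.7 says that the guidelines in Table 6-2 should be followed if non-infectious pneumonitis develops. Table 6-2 then gives:

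- Grade 2, management column: "Prescribe corticosteroids if symptoms are troublesome".
- Grade 2, everolimus dose-adjustment column: "Consider interruption of therapy, rule out infection and consider treatment with corticosteroids until symptoms improve to grade < 1". The same cell adds "Discontinue treatment if failure to recover within 4 wks".
- Grades 3 and 4, management column: "Prescribe corticosteroids if infective origin is ruled out. Taper as medically indicated".
- Grade 3, dose-adjustment column: everolimus may restart one level lower after recovery within 4 weeks if there is clinical benefit.

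The body text of Section 6.1.4.7 says instead that everolimus stops permanently at grade 3 or higher. Table 6-8, in its row for grade 3 non-hematological toxicity, tells the site to consider a brief course of corticosteroids for pneumonitis and gives no length.

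**The concern.** A site treating pneumonitis has two current instructions that do not refer to each other. One sets a limit of 2 weeks; the other sets none. Since the same list makes room for adverse-event treatment in two other bullets, a site is likely to read the corticosteroid bullet as unconditional. Protocol Section 12 adds that deviations cannot be authorized on request.

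The first thing at stake is consistent management of a recognised toxicity. The second is how the data are classified. Protocol violation is a listed ground for withdrawal in Section 7.1.4.1, and discontinuation before the 9-month assessment counts as not progression-free (Protocol Section 10.4.3; SAP Section 6.3.1). A deviation given severity code 1 in VAP Module 3 removes the patient from the per-protocol set (SAP Section 3.5). The documents provided do not settle how a long course given under Table 6-2 would be coded.

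**Working it through.** The plan states no figure to reproduce. The check is a comparison of texts and time limits.

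**Time limits**

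- Section 6.4.3: 2 weeks × 7 = 14 days. Anything longer is prohibited.
- Table 6-2: no limit on corticosteroid duration in any row.
- Table 6-2, grades 2 and 3: 4 weeks × 7 = 28 days. This figure stands in the everolimus dose-adjustment column and is the time allowed for recovery before everolimus is stopped. It is not a corticosteroid duration.
- Table 6-8, grade 3: brief course, length undefined.

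**Where the rules part**

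| Course length | Section 6.4.3 | Table 6-2 |
|---|---|---|
| 14 days or less | allowed | not excluded |
| 15 to 28 days | prohibited | not excluded; still inside the everolimus recovery window |
| more than 28 days | prohibited | not excluded by any stated limit on corticosteroids |

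The two sections collide only above 14 days. In the 15-to-28-day band a patient can also recover and restart everolimus as Table 6-2 provides.

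**By grade**

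- Grade 1 is radiographic only and Table 6-2 calls for no specific therapy, so there is no conflict.
- Grade 2: corticosteroids are conditional and run to a symptom endpoint rather than a date. The conflict can arise, and the patient can stay on study.
- Grade 3: the taper is open-ended. Whether the patient stays on study depends on which text governs, because the body of Section 6.1.4.7 ends everolimus permanently and Table 6-2 allows a restart. Table 6-8 points to a brief course for the same event.
- Grade 4: everolimus is discontinued. Section 6.3.2 treats a patient who stops study drug as withdrawn after the final visit, and stops the combination if either component stops. The prohibition then has little practical effect.

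**By arm**

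Section 6.1.4.7 attributes the pneumonitis risk to everolimus, so arms 2 and 3 carry most of the exposure. This is an inference. Table 6-2 applies to any patient with non-infectious pneumonitis, and Section 6.4.3 covers all three arms.

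**The case against.** The strongest reply is that this is a missing cross-reference and little more. Most of its parts stand.

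- A course of 14 days or less satisfies every section, and the brief course in Table 6-8 fits comfortably within the limit. That narrows the conflict. It does not remove it, because Table 6-8 gives no length, covers only grade 3, and differs from Table 6-2 for that same grade.
- No text makes withdrawal compulsory. Where Section 6.4.3 requires a patient to leave, it says so, as for QT-prolonging drugs and other anticancer agents. Protocol violation is only a discretionary ground in Section 7.1.4.1, and Section 12.1 expects immediate safety action even if it deviates from the protocol. This stands.
- Exclusion from the per-protocol set is not established. The violations named in Protocol Section 10.1.3 do not include corticosteroid use. The list is open and defers to the VAP document, which is not among the documents provided. The per-protocol analysis of the primary endpoint is exploratory in any case.

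Three stronger readings are tempting. A reader might take the 4 weeks in Table 6-2 as a permitted corticosteroid duration; it is the everolimus recovery window. A reader might apply the incidence of at least 1/10 in Protocol Section 1.2.2.3 to arms of 41 and 42 and obtain about 4 patients per arm. That rate covers all grades in pooled oncology data, so it includes grade 1 cases that need no therapy, and it says nothing about courses over 14 days. Finally, the everolimus and combination arms finished exactly on their cut-offs (14/42 and 13/41; Amendment 5 rationale and SAP Section 6.3.2), so a reader might infer that one withdrawal under this rule would change a decision. Both arms had already met their cut-offs, this mechanism could only have removed successes, and no such case is documented.

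**Conclusion.** The conflict is real and in current text. A corticosteroid course longer than 14 days, given for pneumonitis as Table 6-2 permits, is prohibited by Section 6.4.3, and nothing in the protocol says which prevails. It would be too strong to say that properly treated patients breach the protocol in general, or that only the everolimus arms are touched.

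The size cannot be calculated: the documents give no distribution of corticosteroid duration and no pneumonitis rate for this population. The finding assumes only that some courses under Table 6-2 exceed 14 days, which its wording allows. It does not disturb the completed primary analysis. What remains open is the handling of patients still on treatment in the extension (11 at Amendment 5) and the per-protocol classification, which SAP Sections 3.5 and 3.8 allow to be revisited before the extension database lock and which feeds the per-protocol analysis of progression-free survival in SAP Section 7.1. It is a clarification worth making because it touches the management of a toxicity and costs little.

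**What to change.** Reconcile Section 6.4.3 with Section 6.1.4.7, Table 6-2 and the grade 3 row of Table 6-8. The protocol should state either that corticosteroids given for pneumonitis under Table 6-2 fall outside the 2-week prohibition, or that Table 6-2 is subject to it, with a cross-reference in both places. In the same edit, resolve the grade 3 conflict between permanent discontinuation in the text of Section 6.1.4.7 and restart in Table 6-2. These are clinical rules for the sponsor's clinical team to decide; this review does not favour either option.

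Then make the deviation coding in VAP Module 3 follow the reconciled rule, so that treatment given in accordance with Table 6-2 is not coded as a violation. Check any extension-phase records already coded.

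The cost is a sentence or two in the protocol for each of the two conflicts and one line in the deviation specification. No new data or analysis is needed.

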6.5 Patient numbering, treatment assignment and randomization

6.5.1 Patient numbering

Each patient is identified in the study by a Subject Number (Subject No.), that is assigned when the patient is first enrolled for screening and is retained as the primary identifier for the patient throughout his/her entire participation in the trial. The Subject No. consists of the 4-digit Center Number (Center No.) (as assigned by Novartis to the investigational site) with a 5-digit sequential patient number suffixed to it, so that each subject is numbered uniquely across the entire database.

Upon signing the ICF, the patient number is assigned by the investigator. At each site, the first patient is assigned patient number 00001, and subsequent patients are assigned consecutive numbers (e.g. the second patient is assigned patient number 00002, the third patient is assigned patient number 00003).

Once assigned, the Subject No. must not be reused for any other subject and the Subject No. for that individual must not be changed, even if the patient is re-screened.

6.5.2 Treatment assignment and randomization

Patients will be assigned to one of the 3 treatment arms ([Section 4.1](#) and [Section 6.1](#)) in a ratio of 1:1:1.

Stratification: Randomization will be stratified by typical carcinoid tumor (TC) vs. atypical carcinoid tumor (AC) according to WHO classification and line of study treatment (1st line vs. others). In case of naïve patients, the study treatment will be considered as 1st line. The randomization scheme will be reviewed by a Biostatistics Quality Assurance Group.

Randomization: The randomization numbers will be generated using the following procedure to ensure that treatment assignment is unbiased and concealed from patients and investigator staff. A patient randomization list will be produced by the IVRS provider using a validated system that automates the random assignment of patient numbers to randomization numbers. These randomization numbers are linked to the different treatment arms.

The patient number will be entered into the IVRS system by the site, the randomization number and treatment arm linked to this patient number will be allocated by the system; IVRS will communicate to the site personnel only the treatment arm assigned while the randomization number linked to this will not be communicated. The randomization number will be stored in the IVRS databases and only provided to authorised trial personnel on request. Prior to dosing and at the end of the screening period, all patients who fulfill all inclusion/exclusion criteria will be randomized via IVRS/IWRS to one of the treatment arms. The investigator or his/her delegate will call or log on to the IVRS/IWRS and confirm that the patient fulfils all the inclusion/exclusion criteria. The IVRS will assign the patient one of the treatment arm.

6.5.3 Treatment blinding

Not applicable.

6.6 Study drug supply

6.6.1 Study drug preparation and dispensation

Study medication will be dispensed by an authorized person at the investigator's site. Patients will receive either pasireotide LAR alone and everolimus alone or a combination of pasireotide LAR and everolimus depending on the treatment arm they were randomized to.

All dosages prescribed and dispensed to the patient and all dose changes during the study must be recorded on the CRF.

Table 6-12 Preparation and dispensing

Study drugs	Dispensing	Preparation
Pasireotide LAR	i.m. injection performed by study nurse or study physician every 28 days (+/- 3 days) on an outpatient basis	See below
Everolimus	Tablets including instructions for administration are dispensed by study personnel on an outpatient basis. Patients will be provided with adequate supply of study treatment for self-administration at home until at least their next scheduled study visit.	Not applicable

6.6.1.1 Preparation procedure for pasireotide LAR

The reconstitution of pasireotide LAR has to be performed just prior to administration. The i.m. injection must be given immediately after the withdrawal of the reconstituted suspension from the vial in the syringe.

Table 6-13 Handling and preparation of pasireotide LAR dose

[figure not shown]
Dose (mg)	Volume to be injected
20	1 x 20 mg vial + 2 mL vehicle: whole volume to be injected
20	1 x 40 mg vial + 2 mL vehicle: 0.9 mL of volume to be injected
40	1 x 40 mg vial + 2 mL vehicle: whole volume to be injected
60	1 x 60 mg vial + 2 mL vehicle: whole volume to be injected

60 mg dosage strength (60 mg per vial)

- Take one (1) pasireotide LAR 60 mg vial.
- Remove the transparent flip-off cap from the vial.
- Take one vehicle ampoule and break off the upper part.
- Withdraw the content of the vehicle ampoule with a needle and the 3 mL syringe (or 2.5 mL syringe, in case the 3mL syringe is not available).
- Remove air bubbles by pushing the piston and wipe the needle with a sterile pad and adjust the volume to 2 mL.
- Inject 2 mL of vehicle into the vial containing the powder (60 mg)
- Shake the vial up and down for at least 30 seconds in order to get a homogenous suspension.
- Withdraw the whole volume of suspension from the vial with a needle and the 3 mL (or 2.5 ml) syringe.
- Reverse the syringe and aspirate in the suspension contained in the needle to the syringe.
- Change the needle with a standard i.m. injection needle.
- Remove air bubbles by pushing the piston and wipe the needle with a sterile pad.
- Immediately, inject the whole volume of suspension intra-muscularly to the patient.

40 mg dosage strength (40 mg per vial)

- Take one (1) pasireotide LAR 40 mg vial.
- Remove the transparent flip-off cap from the vial.

- Take one vehicle ampoule and break off the upper part.
- Withdraw the content of the vehicle ampoule with a needle and the 3 mL syringe (or 2.5 mL syringe, in case the 3 mL syringe is not available).
- Remove air bubbles by pushing the piston and wipe the needle with a sterile pad and adjust the volume to 2 mL.
- Inject 2 mL of vehicle into the vial containing the powder (40 mg).
- Shake the vial up and down for at least 30 seconds in order to get a homogenous suspension.
- Withdraw the whole volume of suspension from the vial with a needle and the 3 mL (or 2.5 mL) syringe.
- Reverse the syringe and aspirate in the suspension contained in the needle to the syringe.
- Change the needle with a standard i.m. injection needle.
- Remove air bubbles by pushing the piston and wipe the needle with a sterile pad.
- Immediately inject the whole volume of suspension intra-muscularly to the patient.

20 mg dosage strength (20 mg per vial)

- Take one (1) pasireotide LAR 20 mg vial.
- Remove the transparent flip-off cap from the vial.
- Take one vehicle ampoule and break off the upper part.
- Withdraw the content of the vehicle ampoule with a needle and the 3 mL syringe (or 2.5 mL, in case the 3 mL syringe is not available).
- Remove air bubbles by pushing the piston and wipe the needle with a sterile pad and adjust the volume to 2 mL.
- Inject 2 mL of vehicle into the vial containing the powder (20 mg)
- Shake the vial up and down for at least 30 seconds in order to get a homogenous suspension.
- Withdraw the whole volume of suspension from the vial with a needle and the 3 mL (or 2.5 mL) syringe.
- Reverse the syringe and aspirate in the suspension contained in the needle to the syringe.
- Change the needle with a standard i.m. injection needle.
- Remove air bubbles by pushing the piston and wipe the needle with a sterile pad.
- Immediately, inject the whole volume of suspension intra-muscularly to the patient.

20 mg dosage strength (40 mg per vial)

- Take one (1) pasireotide LAR 40 mg vial.
- Remove the transparent flip-off cap from the vial.
- Take one vehicle ampoule and break off the upper part.
- Withdraw the content of the vehicle ampoule with a needle and the 3 mL syringe (or 2.5 mL, in case 3ml syringe is not available).

- Remove air bubbles by pushing the piston and wipe the needle with a sterile pad and adjust the volume to 2 mL.
- Inject 2 mL of vehicle into the vial containing the powder (40 mg).
- Shake the vial up and down for at least 30 seconds in order to get a homogenous suspension.
- Withdraw the whole volume of suspension from the vial with a needle and the 3 mL (or 2.5 mL) syringe.
- Reverse the syringe and aspirate in the suspension contained in the needle to the syringe.
- Adjust the volume in the syringe to 0.9 mL.
- Change the needle with a standard i.m. injection needle.
- Remove air bubbles by pushing the piston and wipe the needle with a sterile pad.
- Immediately, inject the whole volume of suspension intra-muscularly to the patient.

6.6.1.2 Everolimus administration

Everolimus will be dispensed by the study center personnel on an outpatient basis. Patients will be provided with an adequate supply of everolimus for self-administration at home.

The investigator should instruct the patient to take the study drug exactly as prescribed (promote compliance).

The patient will take the first dose of everolimus at the center. Everolimus will be dosed starting on Day 1 (Visit 2). Patients will be instructed to take one 10 mg tablet or, alternatively, two 5 mg tablets of everolimus QD orally with a glass of water, at the same time each day either consistently with food or consistently without food. Any dietary habits around the time of everolimus intake should be as consistent as possible throughout the study. The tablet/tablets should be swallowed as a whole and not be chewed or crushed. In cases where the tablet/tablets can not be swallowed, it/they should be disintegrated in water just prior being taken. Approximately 30 mL of water should be put into a glass. The tablet/tablets should then be added and the contents stirred gently (for a maximum of 7 minutes) until the tablet/tablets are disintegrated. The contents should then be drunk. Afterwards, the glass should be rinsed with an additional 30 mL of liquid and drunk.

If vomiting occurs, no attempt should be made to replace the vomited dose unless two everolimus tablets (or one 10 mg tablet) are clearly visible. If two everolimus tablets (or one 10 mg tablet) are clearly visible, then the patient should replace the everolimus dose. Patients should be instructed that if they miss a dose on one day, they must not take any extra dose the next day, but instead to immediately contact the study center as soon as possible to ask for advice.

If the patient misses a dose at the scheduled time, the administration of the study drug can:

- occur within 8 hours after the normal time of administration, and the new time of administration can be considered as a reference for the next administration (eg. if the normal time of administration is 8 am, the 8 am missing dose could be administered by 4 pm of the same day)
- or

- be skipped until the next day.

On days on which there are visits scheduled, patients should be reminded not to take their study drug until advised to do so during the visit. At visits, when laboratory blood samples are drawn, patients should not take the daily study drug dose until the blood sample has been drawn and after all safety assessments have been performed.

Patients are to bring their unused everolimus, as well as the empty blister packs, to the clinic on each visit, and a new pack of everolimus will be dispensed on that visit. Compliance should be verified by the investigator's staff by counting the number of tablets consumed between visits.

The investigator (or his/her designee) will document dosage administration and all dose changes during the study in the CRF. The site must maintain an overall drug accountability log for the study, as well as individual accountability records for each patient. The dose, amount dispensed, amount received, and amount remaining unused must be recorded in the source document. Drug accountability will be noted by the field monitor during site visits and at the completion of the study.

The patient will be asked to return all unused everolimus tablets at each study visit.

Patients will receive treatment with study drug during the duration of the study, or until progressive disease occurs, or until the occurrence of unacceptable toxicity, or until the investigator or patient decides that continuation is not in the best interest of the patient.

Interruption for toxicity should follow the instructions in [Table 6-8](#).

